12.7.3 Assessment of Urinary Function

Urinary function is assessed by comparison of pre- and post-operative UCLA-EPIC Urinary Domain ([Wei et al., 2000](#)), IPSS ([Barry et al., 1992](#)), and IPSS-QoL scores ([Rees, 2013](#)).

Summary statistics will be presented for the timepoints where the questionnaires are collected (baseline, 1, 3, 6, 9, and 12 month follow-up). Additionally, all the follow-up changes from baseline will also be presented, along with the associated paired t-test value.

² Note: Subjects with early positive out-of-field biopsies will not be considered failures for the primary efficacy endpoint.

12.7.3.1 UCLA-EPIC Urinary Domain

For the purpose of assessing the urinary function, the UCLA-EPIC Urinary Domain will be used. This domain consists in 12 items and 4 subscales (Function [5 items], Bother [7 items], Incontinence [4 items], and Irritative/Obstructive [7 items]).

The response for each item is standardized from 0 to 100. The scores for the domain and subscales are the average of the standardized values. If $\geq 20\%$ of the items of a domain score or subscale are missing a response, the corresponding domain summary or subscale cannot be calculated. For the Urinary Domain the minimum number of answers is 10, for Function subscale the minimum number of answers is 4, for the Bother subscale the minimum number of answers is 6, for the Incontinence subscale the minimum number of answers is 4, and for Irritative/Obstructive the minimum number of answers is 6.

For the Function subscale, the following questions are considered ([Table 4](#)):

Table 4 Function subscale questions

Question	Possible answers	Item Response Value	Standardized Value
Over the past 4 weeks, how often have you leaked urine?	More than once a day	1	0
	About once a day	2	25
	More than once a week	3	50
	About once a week	4	75
	Rarely or never	5	100
Over the past 4 weeks, how often have you urinated blood?	More than once a day	1	0
	About once a day	2	25
	More than once a week	3	50
	About once a week	4	75
	Rarely or never	5	100
Over the past 4 weeks, how often have you had pain or burning with urination?	More than once a day	1	0
	About once a day	2	25
	More than once a week	3	50
	About once a week	4	75
	Rarely or never	5	100
Which of the following best describes your urinary control during the last 4 weeks?	No urinary control whatsoever	1	0
	Frequent dribbling	2	33
	Occasional dribbling	3	67
	Total control	4	100
How many pads or adult diapers per day did you usually use to control leakage during the last 4 weeks?	None	0	100
	1 pad per day	1	67
	2 pads per day	2	33
	3 or more pads per day	3	0

For the Bother subscale, the following questions are considered ([Table 5](#)):

Table 5 Bother subscale questions

Question	Possible answers	Item Response Value	Standardized Value
How big a problem, if any, has each of the following been for you during the last 4 weeks?			
Dripping or leaking urine	No problem	0	100
	Very small problem	1	75
	Small problem	2	50
	Moderate problem	3	25
	Big problem	4	0
Pain or burning on urination	No problem	0	100
	Very small problem	1	75
	Small problem	2	50
	Moderate problem	3	25
	Big problem	4	0
Bleeding with urination	No problem	0	100
	Very small problem	1	75
	Small problem	2	50
	Moderate problem	3	25
	Big problem	4	0
Weak urine stream or incomplete emptying	No problem	0	100
	Very small problem	1	75
	Small problem	2	50
	Moderate problem	3	25
	Big problem	4	0
Waking up to urinate	No problem	0	100
	Very small problem	1	75
	Small problem	2	50
	Moderate problem	3	25
	Big problem	4	0
Need to urinate frequently during the day	No problem	0	100
	Very small problem	1	75
	Small problem	2	50
	Moderate problem	3	25
	Big problem	4	0
Overall, how big a problem has your urinary function been for you during the last 4 weeks?	No problem	1	100
	Very small problem	2	75
	Small problem	3	50

Question	Possible answers	Item Response Value	Standardized Value
	Moderate problem	4	25
	Big problem	5	0

For the Incontinence subscale, the following questions are considered ([Table 6](#)):

Table 6 Incontinence subscale questions

Question	Possible answers	Item Response Value	Standardized Value
Over the past 4 weeks, how often have you leaked urine?	More than once a day	1	0
	About once a day	2	25
	More than once a week	3	50
	About once a week	4	75
	Rarely or never	5	100
Which of the following best describes your urinary control during the last 4 weeks?	No urinary control whatsoever	1	0
	Frequent dribbling	2	33
	Occasional dribbling	3	67
	Total control	4	100
How many pads or adult diapers per day did you usually use to control leakage during the last 4 weeks?	None	0	100
	1 pad per day	1	67
	2 pads per day	2	33
	3 or more pads per day	3	0
How big a problem, if any, has each of the following been for you during the last 4 weeks?			
Dripping or leaking urine	No problem	0	100
	Very small problem	1	75
	Small problem	2	50
	Moderate problem	3	25
	Big problem	4	0

For the Irritative/Obstructive subscale, the following questions are considered ([Table 7](#)):

Table 7 Irritative/Obstructive subscale questions

Question	Possible answers	Item Response Value	Standardized Value
Over the past 4 weeks, how often have you urinated blood?	More than once a day	1	0
	About once a day	2	25
	More than once a week	3	50
	About once a week	4	75

Question	Possible answers	Item Response Value	Standardized Value
	Rarely or never	5	100
Over the past 4 weeks, how often have you had pain or burning with urination?	More than once a day	1	0
	About once a day	2	25
	More than once a week	3	50
	About once a week	4	75
	Rarely or never	5	100
How big a problem, if any, has each of the following been for you during the last 4 weeks?			
Pain or burning on urination	No problem	0	100
	Very small problem	1	75
	Small problem	2	50
	Moderate problem	3	25
	Big problem	4	0
Bleeding with urination	No problem	0	100
	Very small problem	1	75
	Small problem	2	50
	Moderate problem	3	25
	Big problem	4	0
Week urine stream or incomplete emptying	No problem	0	100
	Very small problem	1	75
	Small problem	2	50
	Moderate problem	3	25
	Big problem	4	0
Waking up to urinate	No problem	0	100
	Very small problem	1	75
	Small problem	2	50
	Moderate problem	3	25
	Big problem	4	0
Need to urinate frequently during the day	No problem	0	100
	Very small problem	1	75
	Small problem	2	50
	Moderate problem	3	25
	Big problem	4	0

For the Urinary Domain, all questions will be considered (without repeating them, see [Table 8](#)) ([Wei et al., 2000](#)).

Table 8 Urinary domain questions

Question	Possible answers	Item Response Value	Standardized Value
Over the past 4 weeks, how often have you leaked urine?	More than once a day About once a day More than once a week About once a week Rarely or never	1 2 3 4 5	0 25 50 75 100
Over the past 4 weeks, how often have you urinated blood?	More than once a day About once a day More than once a week About once a week Rarely or never	1 2 3 4 5	0 25 50 75 100
Over the past 4 weeks, how often have you had pain or burning with urination?	More than once a day About once a day More than once a week About once a week Rarely or never	1 2 3 4 5	0 25 50 75 100
Which of the following best describes your urinary control during the last 4 weeks?	No urinary control whatsoever Frequent dribbling Occasional dribbling Total control	1 2 3 4	0 33 67 100
How many pads or adult diapers per day did you usually use to control leakage during the last 4 weeks?	None 1 pad per day 2 pads per day 3 or more pads per day	0 1 2 3	100 67 33 0
How big a problem, if any, has each of the following been for you during the last 4 weeks?			
Dripping or leaking urine	No problem Very small problem Small problem Moderate problem Big problem	0 1 2 3 4	100 75 50 25 0
Pain or burning on urination	No problem Very small problem Small problem Moderate problem Big problem	0 1 2 3 4	100 75 50 25 0

Question	Possible answers	Item Response Value	Standardized Value
Bleeding with urination	No problem Very small problem Small problem Moderate problem Big problem	0 1 2 3 4	100 75 50 25 0
Weak urine stream or incomplete emptying	No problem Very small problem Small problem Moderate problem Big problem	0 1 2 3 4	100 75 50 25 0
Waking up to urinate	No problem Very small problem Small problem Moderate problem Big problem	0 1 2 3 4	100 75 50 25 0
Need to urinate frequently during the day	No problem Very small problem Small problem Moderate problem Big problem	0 1 2 3 4	100 75 50 25 0
Overall, how big a problem has your urinary function been for you during the last 4 weeks?	No problem Very small problem Small problem Moderate problem Big problem	1 2 3 4 5	100 75 50 25 0

12.7.3.2 IPSS

For the purpose of assessing the urinary function, the IPSS will be used. It consists of 8 questions, the first 7 related to severity of a range of urinary symptoms (three storage symptoms [urgency, frequency and nocturia] and four voiding symptoms [weak stream, hesitancy, intermittency and straining]) – scoring from 1 to 5 for each question to make a maximum total score of 35. Questions are detailed in [Table 9](#), along with correspondent answers and respective item response value.

Table 9 IPSS questions

Question	Possible answers	Item Response Value
1.Over the past month, how often have you had a sensation of not emptying your bladder completely after you finished urinating?	Not at all Less than 1 time in 5 Less than half the time About half the time More than half the time Almost always	0 1 2 3 4 5
2.Over the past month, how often have you had to urinate again less than 2 hours after you finished urinating?	Not at all Less than 1 time in 5 Less than half the time About half the time More than half the time Almost always	0 1 2 3 4 5
3.Over the past month, how often have you found that you stopped and started again several times when you urinated?	Not at all Less than 1 time in 5 Less than half the time About half the time More than half the time Almost always	0 1 2 3 4 5
4.Over the past month, how often have you found it difficult to postpone urination?	Not at all Less than 1 time in 5 Less than half the time About half the time More than half the time Almost always	0 1 2 3 4 5
5.Over the past month, how often have you had a weak stream?	Not at all Less than 1 time in 5 Less than half the time About half the time More than half the time Almost always	0 1 2 3 4 5
6.Over the past month, how often have you had to push or strain to begin urination?	Not at all Less than 1 time in 5 Less than half the time About half the time More than half the time	0 1 2 3 4

Question	Possible answers	Item Response Value
	Almost always	5
7. Over the past month or so, how many times did you get up to urinate from the time you went to bed until the time you got up in the morning?	None	0
	1 time	1
	2 times	2
	3 times	3
	4 times	4
	5 or more times	5

The total score will be the sum of all item scores. The total symptom score will be stratified as Mild (total score between 0 and 7), Moderate (from 8 to 19), and Severe (from 20 to 35). All items must be completed, no missing items are acceptable ([Barry et al., 1992](#)).

12.7.3.2.1 IPSS-QoL

For the purpose of assessing the urinary function, the IPSS-QoL will be used. It consists of a single question that assesses the impact of the symptoms detailed in IPSS on the subject's quality of life. Subjects select a score from zero (0) indicating delighted to six (6) indicating terrible ([Rees, 2013](#)), as detailed in [Table 10](#).

Table 10 IPSS-QoL question

Question	Possible answers	Item Response Value
If you were to spend the rest of your life with your urinary condition just the way it is now, how would you feel about that?	Delighted	0
	Pleased	1
	Mostly satisfied	2
	Mixed about equally satisfied and dissatisfied	3
	Mostly dissatisfied	4
	Unhappy	5
	Terrible	6

12.7.4 Assessment of Erectile Function

For the purpose of assessing erectile function, the IIEF-15 questionnaire will be used. Summary statistics will be presented for the timepoints where the questionnaires are collected (baseline, 1, 3, 6, 9, and 12 month follow-up). Additionally, all the follow-up changes from baseline will also be presented, along with the associated paired t-test value.

The questionnaire consists of 15 questions, where 6 are related to erectile function, 3 refer to satisfaction with intercourse, 2 are related to orgasmic function, 2 refer to sexual desire, and 2 refer to overall sexual satisfaction.

The items are not weighted and total scores range from 5 to 75. The domain scores are computed by summing the scores for each individual item in each domain. The subscales range as follows: Erectile Function (1-30), Intercourse Satisfaction (0-15), Orgasmic Function (0-10), Sexual Desire (2-10), and Overall Sexual Satisfaction (2-10). On the Erectile Function subscale, lower scores indicate worse erectile

dysfunction, while on the remaining subscales, higher scores indicate less dysfunction. The overall score considers all questions. All items must be completed, no missing values are acceptable ([Rosen et al., 2002](#)).

For the Erectile Function subscale, the following questions are considered ([Table 11](#)):

Table 11 Erectile Function subscale questions

Question	Possible answers	Item Response Value
Over the last four weeks, how often were you able to get an erection during sexual activity?	No sexual activity Almost never or never A few times (less than half the time) Sometimes (about half the time) Most times (more than half the time) Almost always or always	0 1 2 3 4 5
Over the last four weeks, when you had erections with sexual stimulation, how often were your erections hard enough for penetration?	No sexual activity Almost never or never A few times (less than half the time) Sometimes (about half the time) Most times (more than half the time) Almost always or always	0 1 2 3 4 5
Over the last four weeks, when you attempted intercourse, how often were you able to penetrate (enter) your partner?	No sexual activity Almost never or never A few times (less than half the time) Sometimes (about half the time) Most times (more than half the time) Almost always or always	0 1 2 3 4 5
Over the last four weeks, during sexual intercourse, how often were you able to maintain your erection after you had penetrated (entered) your partner?	No sexual activity Almost never or never A few times (less than half the time) Sometimes (about half the time) Most times (more than half the time) Almost always or always	0 1 2 3 4 5
Over the last four weeks, during sexual intercourse, how difficult was it to maintain your erection to completion of intercourse?	Did not attempt intercourse Extremely difficult Very difficult Difficult Slightly difficult Not difficult	0 1 2 3 4 5
Over the last four weeks, how do you rate your confidence that you can get and keep your erection?	Very low Low	1 2

Question	Possible answers	Item Response Value
	Moderate	3
	High	4
	Very high	5

For the Intercourse Satisfaction subscale, the following questions are considered ([Table 12](#)):

Table 12 Intercourse Satisfaction subscale questions

Question	Possible answers	Item Response Value
Over the last four weeks, how many times have you attempted sexual intercourse?	No attempts	0
	1-2 times	1
	3-4 times	2
	5-6 times	3
	7-10 times	4
	11 or more times	5
Over the last four weeks, when you attempted sexual intercourse how often was it satisfactory for you?	Did not attempt intercourse	0
	Almost never or never	1
	A few times (less than half the time)	2
	Sometimes (about half the time)	3
	Most times (more than half the time)	4
	Almost always or always	5
Over the last four weeks, how much have you enjoyed sexual intercourse?	No intercourse	0
	No enjoyment at all	1
	Not very enjoyable	2
	Fairly enjoyable	3
	Highly enjoyable	4
	Very highly enjoyable	5

For the Orgasmic Function subscale, the following questions are considered ([Table 13](#)):

Table 13 Orgasmic Function subscale questions

Question	Possible answers	Item Response Value
Over the last four weeks, when you had sexual stimulation or intercourse, how often did you ejaculate?	No sexual stimulation or intercourse	0
	Almost never or never	1
	A few times (less than half the time)	2
	Sometimes (about half the time)	3

Question	Possible answers	Item Response Value
Over the last four weeks, when you had sexual stimulation or intercourse, how often did you have the feeling of orgasm or climax?	Most times (more than half the time)	4
	Almost always or always	5
	Almost never or never	1
	A few times (less than half the time)	2
	Sometimes (about half the time)	3
	Most times (more than half the time)	4
	Almost always or always	5

For the Sexual Desire subscale, the following questions are considered ([Table 14](#)):

Table 14 Sexual Desire subscale questions

Question	Possible answers	Item Response Value
Over the last four weeks, how often have you felt sexual desire?	Almost never or never	1
	A few times (less than half the time)	2
	Sometimes (about half the time)	3
	Most times (more than half the time)	4
	Almost always or always	5
Over the last four weeks, how would you rate your level of sexual desire?	Very low or none at all	1
	Low	2
	Moderate	3
	High	4
	Very high	5

For the Overall Sexual Satisfaction subscale, the following questions are considered ([Table 15](#)):

Table 15 Overall Sexual Satisfaction subscale questions

Question	Possible answers	Item Response Value
Over the last four weeks, how satisfied have you been with your overall sex life?	Very dissatisfied	1
	Moderately dissatisfied	2
	Equally satisfied and dissatisfied	3
	Moderately satisfied	4
	Very satisfied	5
Over the last four weeks, how satisfied have you been with your sexual relationship with your partner?	Very dissatisfied	1
	Moderately dissatisfied	2
	Equally satisfied and dissatisfied	3

Question	Possible answers	Item Response Value
	Moderately satisfied	4
	Very satisfied	5

12.7.5 Effectiveness of Therapy by Measurement of PSA Kinetics

The mean PSA levels at each visit, the overall percent reduction in PSA levels (ng/mL) from screening to each visit (1, 3, 6, 9, and 12 month follow-up), and the proportion of subjects with a PSA reduction compared to screening at each visit will be presented. If a subject is re-treated during the study, all PSA values collected following the re-treatment will not be included in the analyses but will be included in the listings. Mean PSA nadir and post-nadir PSA values through 12 months post-treatment will be summarized. Kaplan-Meier analysis and summary statistics for time, including median time to event and associated 95% CI will be presented for PSA nadir. For this assessment, our baseline will be the screening measurements.

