If the subject is re-biopsied, and there is a positive in-field core, this subject will be considered a failure for the primary efficacy endpoint (see Section 6.7). If the subject and the positive lesion still meet all of the inclusion criteria and none of the exclusion criteria⁴ (i.e., the lesion is an intermediate-risk lesion of Gleason 3+4 or 4+3 and all other criteria are met), the subject can be re-treated with the NanoKnife System and will continue to be followed up for the duration of the study for secondary efficacy endpoints and safety. If the subject and their treating physician decide on re-treatment with something other than the NanoKnife System, or if they no longer meet the inclusion/exclusion criteria for the study (i.e., they have a Gleason \geq 4+4 lesion and require whole-gland treatment), their post-re-treatment data will be excluded from the analysis.

Positive Early Out-of-Field Biopsy:

If the subject is re-biopsied, and there is a positive out-of-field core, this will not be considered a failure for the primary efficacy endpoint. If the subject and the new positive lesion still meet all of the inclusion criteria and none of the exclusion criteria⁵ (i.e., the new lesion is an intermediate-risk lesion of Gleason 3+4 or 4+3 and all other criteria are met), the subject can be re-treated for the new lesion with the NanoKnife System as part of the study. If the subject and their treating physician decide on re-treatment with something other than the NanoKnife System, or if they no longer meet the inclusion/exclusion criteria for the study (i.e., the new lesion is Gleason \geq 4+4 and the subject requires whole-gland treatment), they will exit the study though will continue to be followed for safety. These subjects who were re-treated with something other than the NanoKnife System for an out-of-field lesion prior to 12 months will have their post-re-treatment data excluded from the analysis.

Negative Early Biopsy:

If the subject is re-biopsied and there are no positive findings, they will continue in the study as planned, completing follow-up visits and the scheduled mpMRI and biopsy at 12 months.

If a subject is re-treated, regardless of the re-treatment selected, they should be followed up by the treating physician or their primary physician for routine urological care after the completion of the study.

Additional 'For Cause' Tests:

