6.9 Secondary Endpoints

Additional endpoints for statistical consideration will include the following:

- Rate of negative in-field biopsy at 12 months as defined by the Delphi consensus criterion of absence of clinically significant disease (≤ 3 mm of Gleason ≤ 6 disease in any biopsy core is insignificant)¹
- Assessment of urinary function by comparison of pre- and post-operative UCLA Expanded Prostate Cancer Index Composite (UCLA-EPIC) Urinary Domain² and International Prostate Symptom Scores (IPSS)³ and IPSS Quality of Life (IPSS-QoL) scores.
- Assessment of erectile function by comparison of pre- and post-operative 15-Item International Index of Erectile Function (IIEF-15)⁴ potency scores.
- Effectiveness of therapy by measurement of prostate-specific antigen (PSA) kinetics including time to PSA nadir.
- Assessment of changes in prostate volume by comparison of pre-treatment and 12-month prostate volume measured via mpMRI.
- Assessment of ablation effectiveness by evaluation of prostate tissue by mpMRI at 3 months post-treatment and at 12 months post-treatment.

- Assessment of need for secondary or adjuvant treatment following treatment with the NanoKnife System.
- Evaluation of subject reported pre- and post-operative Quality of Life (QoL) using the 5-dimension scale EuroQol (EQ-5D®).⁵

If a subject is re-treated with something other than the NanoKnife System during the study, secondary endpoint data collected during and after the re-treatment will not be included in the secondary endpoint analyses.

Negative in-field biopsy at 12 months as defined by Delphi consensus criteria: Negative in-field biopsy is defined to be the absence of clinically significant disease (≤ 3 mm of Gleason ≤ 6 disease in any biopsy core is insignificant).¹ Prostate cancer that is ≤ 3 mm Gleason 6 will be considered clinically insignificant cancer and will not be considered a positive biopsy for this endpoint.

UCLA-EPIC²: The Urinary domain score from the UCLA-EPIC (University of California Los Angeles Expanded Prostate Cancer Index Composite) Urinary questionnaire will be presented for each visit (i.e., 1, 3, 6, 9, and 12 month follow-up). In addition, the 6-month and 12-month change from baseline will also be tabulated. See **Appendix E – Subject Questionnaires – 1.1 UCLA-EPIC** section for more details on the questionnaire and scoring instructions.

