6.1 Changes from Protocol

There are no plans to further the follow-up beyond the 12 months. The continuation of follow-up for up to 5 years, as standard of care, to assess the rate of progression, re-intervention, and adverse events is not expected at this point. This exploratory endpoint stated in protocol is outside of the scope of this SAP.

No multiple imputation will be used for the missing items for 15-Item International Index of Erectile Function (IIEF-5), International Prostate Symptom Scores (IPSS), and Expanded Prostate Cancer Index Composite (EPIC) questionnaires, as stated in the protocol.

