10.4 PSA Nadir Definition

PSA nadir is the absolute lowest level that PSA achieves after the initial NanoKnife System procedure up until the time of re-treatment, if applicable.

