10.6 Missing Data

Variables will be summarized for all eligible subjects with available data for the majority of endpoints/data (except for the endpoints/data detailed below). Missing data in the CRF will be detected by data management and monitored via edit checks and data analysis. Follow-up to collect missing data will be conducted as outlined in the Site Management Plan.

The following imputation methods will be applied:

- When calculating the proportion of subjects with a negative in-field biopsy, subjects with missing biopsy information post-ablation will be imputed as “positive”.
- Subjects with missing pre- or post-ablation prostate volume measurements will be imputed as having a zero change in volume. In accordance with the secondary endpoint related with “change in prostate volume”, this imputation will only be performed at Month 12 Visit.
- Missing PSA data will be imputed using last observation carried forward (LOCF).

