12.1 Subject Disposition

The number and percentage of subjects screened and included in each analysis set will be presented, together with the number and percentage of subjects who withdrew from the study prematurely and a

breakdown of the corresponding reasons for withdrawal. A tabulation of the number and percentage of subjects enrolled at each center will be presented.

If a subject undergoes re-treatment, one re-treatment with IRE for the same lesion will allow the subject to continue in the study. However, if there is more than one re-treatment with IRE on the same lesion or at least one re-treatment with a type of treatment other than IRE, then the subject will exit the study (data until the moment of re-treatment will be used for analysis) and will only be followed up for safety purposes.

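### SAP 12.7.5 excludes PSA after any re-treatment, while protocol 6.9 and 4.6.16 keep it after NanoKnife re-treatment; the change is undeclared and the handling of excluded values is undefined

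*Combined protocol and SAP*

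**What the plan says.** SAP 12.7.5 summarises mean PSA, percent reduction and the proportion of subjects with a reduction from screening at months 1, 3, 6, 9 and 12. For a subject re-treated during the study, with no limit by type of re-treatment, "all PSA values collected following the re-treatment will not be included in the analyses but will be included in the listings". SAP 10.4 defines the nadir in the same spirit, from the initial procedure "up until the time of re-treatment, if applicable".

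Protocol 6.9 is narrower. Its exclusion covers a subject "re-treated with something other than the NanoKnife System during the study, secondary endpoint data collected during and after the re-treatment will not be included". Protocol 4.6.16 states that a man re-treated with NanoKnife after a positive early in-field biopsy "will continue to be followed up for the duration of the study for secondary efficacy endpoints and safety". PSA kinetics is one of those secondary endpoints.

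The SAP's own general rule, in 12.1, is that "one re-treatment with IRE for the same lesion will allow the subject to continue in the study". It cuts data at re-treatment only for a second IRE on the same lesion or for another type of treatment.

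SAP 6.1 lists two changes from the protocol: the five-year exploratory endpoint is out of scope, and "No multiple imputation will be used for the missing items" of the questionnaires. The PSA rule is not listed. SAP 10.6, like protocol 6.4, adds: "Missing PSA data will be imputed using last observation carried forward (LOCF").

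**The concern.** Two approved documents give different data sets for the same PSA tables, and a reader of SAP 6.1 would not learn of it. The excluded values are not a random subset. Under protocol 4.6.16 an early biopsy is triggered by a PI-RADS 3 or higher lesion on the 3-month mpMRI, by PSA at nadir + 2 ng/mL, or by clinical suspicion, and re-treatment follows a positive core. The exclusion is therefore related to outcome, and it falls mainly on the 6-, 9- and 12-month rows of an analysis presented as effectiveness of therapy.

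There is a second gap. The excluded values were collected and stay in the listings. The SAP does not say whether they count as missing for the carry-forward rule, so two programmers could produce different tables from the same data.

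**Working it through.** **Step 1: compare the rules.**

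| Re-treatment | Protocol 6.9 / 4.6.16 | SAP 12.1 | SAP 12.7.5 (PSA) |
|---|---|---|---|
| First NanoKnife, same lesion | later data kept | subject continues | later PSA excluded |
| First NanoKnife, new out-of-field lesion | allowed within the study; 6.9 does not exclude later data | not listed as a reason for exit | later PSA excluded |
| Second NanoKnife, same lesion | 6.9 does not exclude later data | data cut | later PSA excluded |
| Other treatment | later data excluded | data cut | later PSA excluded |

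The documents agree on other treatments. The PSA conflict is confined to men re-treated with NanoKnife. SAP 12.7.3, 12.7.4 and 12.7.6 contain no such cut, so a man re-treated once with NanoKnife stays in the questionnaire and prostate volume analyses but loses his later PSA.

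**Step 2: see what the choice can do.** The plan states no figure to reproduce. The only input from the documents is the planned 118 subjects. The rest are assumptions, because neither document gives a re-treatment rate or a PSA response rate:

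- m men re-treated with NanoKnife: 2, 6, 12 or 18 (about 2% to 15% of 118);
- PSA below screening at month 12 in 90% of men not re-treated;
- PSA below screening at month 12 in 70% of re-treated men, measured after the re-treatment;
- PSA below screening in 20% to 60% of re-treated men at their last value before re-treatment.

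The formulas for the proportion with a reduction are:

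- dropped: 0.90(118 − m)/(118 − m) = 90.0%;
- protocol 6.9: [0.90(118 − m) + 0.70m]/118;
- carried forward: [0.90(118 − m) + q·m]/118, with q = 0.20 or 0.60.

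For m = 18, protocol 6.9 gives (90.0 + 12.6)/118 = 86.9%. Carry-forward gives (90.0 + 3.6)/118 = 79.3% or (90.0 + 10.8)/118 = 85.4%.

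| m | Dropped | Protocol 6.9 | Carried forward, q = 0.20 | Carried forward, q = 0.60 |
|---|---|---|---|---|
| 2 | 90.0% | 89.7% | 88.8% | 89.5% |
| 6 | 90.0% | 89.0% | 86.4% | 88.5% |
| 12 | 90.0% | 88.0% | 82.9% | 86.9% |
| 18 | 90.0% | 86.9% | 79.3% | 85.4% |

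**Step 3: read the direction.** The gap between dropping and protocol 6.9 is (m/118)(0.90 − 0.70), or 0.3 points for m = 2 and 3.1 points for m = 18. Dropping raises the rate as long as re-treated men respond less often than the others. Carry-forward falls below protocol 6.9 as long as q is under 0.70. So dropping lies above the protocol figure and carry-forward below it, and the SAP does not choose between them.

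**The case against.** The SAP rule can be defended. If the target is the effect of the first ablation, PSA should stop at any re-treatment. Keeping later values credits the second ablation's fall to the first and may flatter the device. SAP 10.4 uses the same window, so the rule looks deliberate. The consequences are also visible elsewhere: early in-field positives are failures in the primary endpoint, SAP 12.7.8 reports the number, reason, location and type of re-treatments, and the excluded PSA values are listed. All of this stands. It supports showing the pre-re-treatment row, but it does not excuse an undeclared departure or settle the carry-forward question.

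A reader might infer three stronger things that the documents do not support.

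- **That failures simply leave the later rows and inflate them.** This holds only if excluded values are dropped. Dropping is arguably the plainer reading, since a collected value is not naturally missing, but the text does not exclude carry-forward, which keeps these men at their last earlier value.
- **That these men were re-treated because PSA or MRI failed.** Under protocol 4.6.16 those findings trigger a biopsy. Re-treatment follows a positive core, which may be out of field and is then not a primary endpoint failure. SAP 12.7.8 does list biochemical progression among the reasons for re-treatment.
- **That every re-treated man has no PSA reduction, which would give a much larger gap.** Nadir + 2 ng/mL is not a rise above screening. With PSA up to 15 ng/mL allowed at entry, and more with low density, a man can meet it and still be below his screening value. Neither document scores re-treated men as not reduced.

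**Conclusion.** The contradiction is real: SAP 12.7.5 conflicts with protocol 6.9 and 4.6.16, is stricter than SAP 12.1, and is not declared in SAP 6.1. It affects only men re-treated with NanoKnife. Their exclusion is related to outcome, but the direction of its effect on the tables is not settled, because the SAP leaves the handling of excluded values open.

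Any size is illustrative. Under the assumptions above, dropping these men overstates the month-12 proportion with a reduction by 0.3 to 3.1 percentage points relative to protocol 6.9. A different re-treatment rate or a different response after re-treatment would change that. No sample size, power or primary endpoint figure is touched. The endpoint is secondary and descriptive, SAP 12.7.5 specifies no test for it, and protocol 6.2 says the study is not powered for secondary claims. The change is worth making because it is cheap and the rules cannot both be followed, not because it threatens the trial's main conclusion.

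**What to change.** - In SAP 12.7.5, report mean PSA, percent reduction and the proportion reduced under the protocol 6.9 rule, with values after NanoKnife re-treatment retained.
- Beside it, show the row limited to values before any re-treatment, with the number of subjects removed at each visit.
- State that PSA values excluded because of re-treatment are not filled by the carry-forward rule in 10.6. If they are to be filled, label that row accordingly.
- List the difference from the protocol in SAP 6.1.
- Leave the nadir definition in 10.4 as it is.

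The cost is SAP wording and one extra row per table, with no new data. SAP 6.0 foresees a final version before database lock, so the change fits the existing process. The downside is that reported PSA figures may become slightly less favourable.
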